4.2.1 Full analysis set (FAS)

The full analysis set (FAS) will include all randomized subjects. Following the intent-to-treat principle, subjects will be analyzed according to the treatment they are assigned to at randomization.

4.2.2 Per-protocol (PP)

Per-protocol population PP consists of all subjects in the FAS who do not have any major protocol violation. The following items will be considered such a major protocol deviations, which will exclude the patient from the PP (Table 2):

CTU Bern	Swiss APERO SAP	Version: 2.0	
	Template: CS_STA_TEM-11	Valid from: 17.08.2021	

Table 2: Derivation of major protocol violations used for PP definition.

Protocol deviation	eCRF sheet	Variable	Variable type	Derivation of violation
Violation of inclusion or exclusion criteria				
Age ≥ 18 years (ic1)	Baseline	age	Continuous	age<18
Written informed consent (ic2)	Baseline	ic2	Binary: yes/no	no
CHADS2VASC score ≥ 2 (ic5)	Baseline	{score based on baseline variables, add points into score}	Add points	hf=yes (1 point), hypertension=yes (1 point), age ≥ 75 (2 points) OR age 65-74 years (1 point), diabetes=yes (1 point), prior_cerebr=yes OR arterial_embolism=yes OR conc_th=yes (2 points), vasculopathy=yes OR prior_mi=yes OR aortic_plaque=yes (1 point), gender=female (1 point). Violation if score<2
HASBLED ≥ 3 or High bleeding risk HBR as defined by Munich consensus document (ic6)	Baseline	{score based on baseline variables, add points into score}	Add points	HASBLED: uncontroll=yes (1 point), kidney_disease=yes (1 point), liverdisease=yes (1 point), type_cerebr=stroke (1 point), priorbleeding=yes OR anemia=yes OR ind_primary={any of: history of major or minor bleeding, wish to avoid triple therapy, risk of fall, concomitant disease improving bleeding risk ,HASBLED ≥ 3 } (1 point) OR hb ≤ 130 g/L in male/hb <120 g/L in female, inab_oac_variability=3 (1 point), age >65 (1 point), bl_drugs_{oac, noac, aspirin, thienopyridine,fans }=any yes (1 point), alcohol=yes (1 point) HBR: priorbleeding=yes OR anemia=yes OR hb ≤ 130 g/L in male/hb <120 g/L in female Violation if score≤ 2 AND HBR=no
Exclusion criteria not met	Randomization	exclusion_criteria_exclusion_crit	Binary: yes/no	no
First LAAC device used not according to randomization	Procedure	first_device, first_imp_att	Categorical, Number	Equal to randomized but implantation attempts = 0 OR
	Procedure	first_device	Categorical	Unequal to randomized

CHADS2VASC: see <https://www.mdcalc.com/cha2ds2-vasc-score-atrial-fibrillation-stroke-risk>

HASBLED: see <https://www.mdcalc.com/has-bled-score-major-bleeding-risk>

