7. STUDY POPULATION

7.1 Eligibility criteria

Participants fulfilling all the following **inclusion criteria** are eligible for the study:

- Written informed consent
- Male or female subject aged 18 years or more with no upper age limit and willing to comply with the protocol
- Indication to a LAA closure as indicated in study population (HAS BLEED ≥ 3 or High bleeding risk as defined by Munich consensus document and CHA2DS2-VASc ≥ 2).

¹ For the definitions of high bleeding risk (HBR) see Appendix 1.

The presence of anyone of the following **exclusion criteria** will lead to exclusion of the participant:

- New York Heart Association class IV congestive heart failure
- ASD or atrial septal repair or closure device
- Single occurrence of AF
- Cardioversion or ablation procedure planned within 30 days
- Implanted mechanical valve prosthesis
- Heart transplantation
- Enrolled in another IDE or IND investigation of a cardiovascular device or an investigational drug
- Female of childbearing potential (age < 50 years and last menstruation within the last 12 months), who did not undergo tubal ligation, ovariectomy or hysterectomy.
- Active infection of any kind
- Severe chronic kidney insufficiency (CrCl < 30 ml/min)
- Terminal illness with life expectancy < 1 year
- Echocardiographic exclusion criteria
- LVEF $< 20\%$
- Intracardiac thrombus or dense spontaneous echo contrast as visualized by TEE within 2 days before implant
- Significant mitral valve stenosis (ie, MV < 1.5 cm 2)
- Complex aortic atheroma with mobile plaque of the descending aorta and/or aortic arch
- Cardiac tumor.

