APPENDIX 1: ENDPOINT AND ADVERSE CLINICAL EVENT DEFINITIONS ²⁴

17.1 INDICATIONS FOR LAAC THERAPY

Potential indications	Example
A. Patient not eligible for long-term OAC therapy (absolute or relative contraindications to OAC)	
1. High bleeding risk (HBR)	
• History of major or minor bleeding (with or without OAC therapy)• Increased risk for bleeding due to physical condition and/or co-morbidities
2. Inability to take OACs for reasons other than high risk for bleeding	
• Intracranial bleeding• GI bleeding• Symptomatic bleeding in critical organ (i.e. ocular, pericardial, spinal cord)• Recurrent epistaxis needing medical attention• Recurrent falls with head trauma and significant musculoskeletal injury• Need for additional dual antiplatelet therapy for CAD and stenting.• Diffuse intracranial amyloid angiopathy• Bowel angiodyplasia• Severe renal insufficiency/haemodialysis• Blood cell dyscrasias• Intolerance• Documented poor adherence to medication• Documented variability in international normalized ratio on warfarin• Higher-risk occupation with increased injury potential• Patient's choice
B. Thromboembolic event or documented presence of thrombus in the LAA despite adequate OAC therapy	
• Embolic stroke or other systemic thromboembolism on adequate OAC therapy with evidence for thrombus origin from the LAA ('malignant LAA')• Documented thrombus formation in the LAA on adequate OAC therapy

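### The SAP's bleeding-risk violation rule scores its own conclusion and narrows the protocol's high-bleeding-risk definition, so per-protocol membership can be wrong in both directions

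*Combined protocol and SAP*

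**What the plan says.** Protocol section 7.1 sets the bleeding and stroke risk criterion as "HAS BLEED ≥ 3 or High bleeding risk as defined by Munich consensus document and CHA2DS2-VASc ≥ 2". Its footnote adds: "For the definitions of high bleeding risk (HBR) see Appendix 1". Appendix 1, section 17.1, gives two elements under high bleeding risk. The first is "History of major or minor bleeding (with or without OAC therapy"; the second is "Increased risk for bleeding due to physical condition and/or co-morbidities".

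Table 2 in SAP section 4.2.2 turns this criterion into a major-violation check with two parts.

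- **The HBR flag** is "HBR: priorbleeding=yes OR anemia=yes OR hb" followed by sex-specific haemoglobin limits. It has no other term.
- **The HAS-BLED score** is a sum of points. The bleeding item can be earned through prior bleeding, anaemia, low haemoglobin or the recorded primary reason for seeking an alternative to anticoagulation. The reasons that count include "history of major or minor bleeding, wish to avoid triple therapy, risk of fall, concomitant disease improving bleeding risk", and the list ends "concomitant disease improving bleeding risk ,HASBLED ≥ 3 } (1 point".

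A patient is a violator, and leaves the per-protocol set, when the score is 2 or less and the flag is negative.

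**The concern.** The check exists to establish from baseline data whether an inclusion criterion was met. Two features undermine that.

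First, the investigator's statement that HAS-BLED is at least 3 adds a point to the score that is meant to verify it. SAP section 5.4 lists this as a category of primary reason, so the field exists and will be used.

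Second, the flag keeps the bleeding-history element of Appendix 1 but reduces the physical-condition and co-morbidity element to anaemia or low haemoglobin. Fall risk and concomitant disease, when they are the primary reason, add one HAS-BLED point but do not set the flag.

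The per-protocol set is more than a spare sensitivity population. SAP section 6.1.2 names it for LAA patency on CCTA and TEE and for device-related thrombosis. Section 6.1.3 lists device-related thrombosis in that set among the main safety outcomes. Protocol section 12.4 adds the primary endpoint and the clinical outcomes.

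**Working it through.** The plan gives no figure for this rule, so the check is a logical one: apply Table 2 to each possible profile and compare the result with section 7.1 and Appendix 1.

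**Inputs.** Let s be the sum of the eight HAS-BLED items other than the bleeding item: uncontrolled hypertension, kidney disease, liver disease, stroke, INR variability, age, drugs and alcohol, one point each. Two of these are "age >65 (1 point), bl_drugs_{oac, noac, aspirin, thienopyridine,fans }=any yes (1 point". Let B be the bleeding item (0 or 1).

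- Score = s + B.
- Violation if s + B ≤ 2 and the flag is negative.

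Protocol section 7.1 is read as (HAS-BLED ≥ 3 or HBR) and CHA2DS2-VASc ≥ 2. Table 2 supports this reading, since it tests the stroke score in a separate row.

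**With the flag negative** (no prior bleeding, anaemia or low haemoglobin), B depends on the primary reason alone. The score is in brackets.

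| Primary reason | s = 0 | s = 1 | s = 2 | s ≥ 3 |
|---|---|---|---|---|
| HAS-BLED ≥ 3, as planned (B = 1) | violation (1) | violation (2) | passes (3) | passes |
| HAS-BLED ≥ 3, circular point removed (B = 0) | violation (0) | violation (1) | violation (2) | passes |
| Fall risk or concomitant disease (B = 1) | violation (1) | violation (2) | passes (3) | passes |
| Rejection of OAC, embolic event under OAC, or other (B = 0) | violation (0) | violation (1) | violation (2) | passes |

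**Wrongly kept.** The first two rows differ only at s = 2. Example: over 65 (1) and on a NOAC (1), so s = 2. The reason HAS-BLED ≥ 3 adds 1, giving 3, and the patient passes. Without the circular point the score is 2 and the patient is a violator, provided no Appendix 1 condition is present.

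**Wrongly excluded.** Take a patient with a physical condition or co-morbidity other than anaemia that qualifies under Appendix 1.

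- If the primary reason earns the point, the patient is excluded whenever s ≤ 1. Example: over 65 (1), reason concomitant disease (1), score 2, flag negative.
- If the primary reason earns no point, the patient is excluded whenever s ≤ 2. Example: over 65 (1), on a listed drug (1), reason rejection of OAC (0), score 2, flag negative.

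Both patients are eligible under Appendix 1.

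**Scale.** The number of such patients is not given. For orientation only, the power for 50% versus 30% at two-sided 5% with n per arm is Φ[(0.20 − 1.96·√(2·0.4·0.6/n)) / √((0.25 + 0.21)/n)].

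- At n = 100: (0.20 − 0.1358)/0.0678 = 0.947, so 82.8%. This agrees with the plan's statement of more than 80%.
- If per-protocol exclusions for all reasons took an assumed 5%, 10% or 20% equally from each arm, power in that set would be 80.8%, 78.7% or 73.7%.

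The share due to this rule is unknown.

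**The case against.** The strongest case against runs as follows.

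- **The definition.** Section 17.1 is a table of indications with examples, and it gives no operational rule for physical condition or co-morbidity. Anaemia is itself a co-morbidity, and several other conditions enter the same check through the score. A reader might infer that the SAP omits half of the protocol definition. The documents do not support that: the second element is narrowed to anaemia. But a score point is not equivalent to the flag, because Appendix 1 makes the condition sufficient by itself.
- **The circular point.** A reader might infer that any patient with the reason HAS-BLED ≥ 3 escapes the check. That is not so: with s of 0 or 1 the patient is still flagged, and with s of 3 or more or a positive flag the point changes nothing. The reason may also reflect an investigator's assessment that the coded fields miss. That would justify querying the record, but not scoring the conclusion.
- **The remedy.** Letting a reason set the flag could look equally self-validating. The difference is that fall risk and concomitant disease are conditions relevant to the definition, while HAS-BLED ≥ 3 is the criterion itself. It remains true that only the primary reason is recorded in that field, so reasons alone would be an incomplete repair. Nor do the documents settle whether the wish to avoid triple therapy belongs under HBR.
- **The baseline table.** One might infer that its HAS-BLED distribution is inflated. SAP section 5.4 does not say that it uses this derivation.
- **Impact.** Eligibility is confirmed before randomisation, the primary analysis follows intention to treat, and no count shows that any patient is affected. All of this stands and limits the weight of the point.

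**Conclusion.** As written, the rule does not implement the protocol criterion and can misclassify per-protocol membership in both directions. The false pass is confined to a negative flag, the reason HAS-BLED ≥ 3, s exactly 2 and no Appendix 1 condition. The false exclusion needs a qualifying condition other than anaemia, no prior bleeding or anaemia, and a score of 2 or less.

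The importance is minor. The consequences are limited to the per-protocol analyses and the reported count of eligibility violations. The inputs are baseline variables, so no difference between arms is expected, and the primary analysis on the full analysis set is unaffected.

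The conclusion rests on two assumptions: that Appendix 1 states the protocol's HBR definition, as the footnote to section 7.1 says, and that the coded fields capture the HAS-BLED items. The consensus document behind Appendix 1 was not available for this review.

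**What to change.** In Table 2 of SAP section 4.2.2:

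1. Delete HAS-BLED ≥ 3 from the primary reasons that earn the bleeding point.
2. Extend the HBR flag to the physical-condition and co-morbidity element of Appendix 1, using recorded baseline fields. Include at least the fall-risk and concomitant-disease reasons, and add co-morbidity fields so that patients whose primary reason is something else are also covered. The sponsor should list the fields that qualify.
3. Check the wish to avoid triple therapy against the cited definition before placing it under the flag or the score.
4. Date and document the corrected rule before unblinded per-protocol results are produced. SAP section 2.8 says the trial statistician is not blinded, so a later change to membership could look data-driven.

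The cost is a revision of one derivation cell and its recoded variables. The fall-risk and concomitant-disease reasons and the co-morbidities tabulated in SAP section 5.4 are already planned for collection, so no new data are needed.

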4.2 Analysis populations

The primary endpoint analysis will be performed using the intention to treat principle on the intention-to-treat, full-analysis set population. Sensitivity analyses will be performed on the per-protocol population. Crossover patients will be considered as a primary end-point event in all analyses.

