6.1 Outcome definitions

Outcomes will be compared randomized to Amulet vs randomized to Watchman.

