6.1.2 Secondary outcome

Secondary outcomes are:

- *LAA patency (arterial and/or venous phase) at 45 day CCTA and 13-month CCTA in the per protocol and as treated populations*
- *All cause of death, stroke, systemic or pulmonary embolism and spontaneous MI*
- *Cardiovascular death*
- *Ischemic stroke*
- *Hemorrhagic stroke*
- *Bleeding events according to the BARC classification at each follow-up.*
- *Procedure-related complications*
- *Rate of patients on (N)OAC at 45 days and 6 months*
- *Device related thrombosis at 45 day TEE/CCTA and 13-month CCTA in the per protocol and as treated populations*
- *Feasibility outcome (number of device implantation attempts, total time procedure, x-ray dose and total contrast dose used in the procedure)*
- *LAA patency at 45 day TEE in the per protocol and as treated populations*

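### The SAP's per-protocol set keeps patients switched to the other device, so its patency-alone and device-thrombosis analyses can count one device's images in the other device's arm

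*Combined protocol and SAP*

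**What the plan says.** SAP 4.2.2 builds the set by subtraction: "Per-protocol population PP consists of all subjects in the FAS who do not have any major protocol violation". Table 2 of that section has one device-related row, "First LAAC device used not according to randomization". Its two triggers read "Equal to randomized but implantation attempts = 0 OR" and "Unequal to randomized". Both concern the first device. No row looks at the device finally implanted, and no row mentions crossover.

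On the arm label, SAP 4.2.1 says of the full analysis set that "subjects will be analyzed according to the treatment they are assigned to at randomization", and SAP 6.1 says "Outcomes will be compared randomized to Amulet vs randomized to Watchman". Section 4.2.2 gives no label of its own.

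On crossovers, SAP 4.2 says "Crossover patients will be considered as a primary end-point event in all analyses".

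On endpoints, SAP 6.1.2 lists "LAA patency (arterial and/or venous phase) at 45 day CCTA and 13-month CCTA in the per protocol and as treated populations". It places 45-day TEE patency and DRT in the same two populations. SAP 6.1.3 repeats DRT, in those populations, as a main safety outcome. Protocol 5.2 and 5.5 agree.

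Protocol 12.4 names per-protocol and as-treated populations but defines neither. SAP 4.2 defines the full analysis, per-protocol and safety sets, but no as-treated set.

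**The concern.** A reader will take a per-protocol imaging result to describe patients who received the device they were allocated. Under Table 2 of SAP 4.2.2 it need not. Take a patient randomised to Watchman/FLX who has two failed attempts and leaves with an Amulet. This patient remains in the set, and the Amulet's patency and thrombus readings would enter the Watchman/FLX arm.

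Two things are at stake: the device contrast for patency without the crossover component, and the attribution of thrombus. DRT is defined in Appendix 1 (17.11) as clot on the device's own surface, so a misplaced case is charged to a device the patient does not carry.

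**Working it through.** **Step 1. Who passes the Table 2 test (SAP 4.2.2).**

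| Situation | First device = randomised? | Attempts with it | In PP? |
|---|---|---|---|
| Other device used first | No | – | No |
| Allocated device named first, never attempted | Yes | 0 | No |
| Allocated device attempted, then other device implanted | Yes | ≥1 | **Yes** |
| Allocated device attempted, no device implanted | Yes | ≥1 | **Yes** |

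Protocol 8.4 and 9.2 call a crossover justified when the allocated device was positioned in the LAA at least once and sealing stayed suboptimal or stability was a concern. That is the third row. The SAP expects such patients: the footnotes to its supplemental tables (5.9) reserve counts for crossover implants in both directions.

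**Step 2. Which arm they count in.** PP is a subset of the full analysis set, which is analysed as randomised, and 6.1 compares outcomes as randomised. Only the safety population (4.2.3) is assigned by the device actually implanted. The randomised label for PP is therefore an inference, but no text points the other way.

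**Step 3. Which endpoints are exposed.** The rule in 4.2 fixes a crossover as a primary-endpoint event whatever the image shows, so the composite is safe. CCTA patency alone (45 days, 13 months), TEE patency (45 days) and DRT have no crossover term. SAP 3.3 derives CCTA patency from attenuation values only, with no reference to the device in place.

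**Step 4. Size.** Inputs: 50% and 30% (SAP 2.3, planning rates for the composite) and 100 per arm (protocol synopsis). The crossover proportions cW and cA are not in the documents, so 2%, 5% and 10% are assumed.

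The plan's own figure first (two-sided 5%, pooled variance under the null):

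[0.20·√100 − 1.96·√(2·0.40·0.60)] / √(0.50·0.50 + 0.30·0.70) = (2.000 − 1.358)/0.678 = 0.947, giving power 82.8%. This agrees with the stated figure of more than 80%, which is not in dispute.

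Now borrow 50% and 30% as device-specific patency, and give switched patients the average patency of the device they carry:

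- Watchman/FLX arm = 50(1 − cW) + 30cW
- Amulet arm = 30(1 − cA) + 50cA
- Difference = 20(1 − cW − cA)

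| Crossover in each arm | Arm rates (%) | Difference, kept | Power, kept (100 per arm) | Power, excluded (n per arm) | Difference, kept, one-way Watchman/FLX→Amulet |
|---|---|---|---|---|---|
| 2% | 49.6 / 30.4 | 19.2 | 79.6% | 82.0% (98) | 19.6 |
| 5% | 49.0 / 31.0 | 18.0 | 74.2% | 80.8% (95) | 19.0 |
| 10% | 48.0 / 32.0 | 16.0 | 63.8% | 78.7% (90) | 18.0 |

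The excluded column assumes that the remaining patients still have rates of 50% and 30%.

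For scale, the 95% confidence half-width at 50% vs 30% is 1.96·√(0.25/100 + 0.21/100) = 13.3 points.

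**Step 5. Direction.** Switched patients are selected for difficult sealing or stability, so the average may not apply to them. With one-way switching of 5% and patency s% among the switched, the Watchman/FLX arm is 47.5 + 0.05s. As s runs from 0 to 100, the difference from 30 runs from 17.5 to 22.5 points. It shrinks only if s is below 50.

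**Step 6. DRT.** Under the same mixing assumption any between-device difference is multiplied by (1 − 2c): 0.96, 0.90, 0.80. The documents give no DRT rate, so no absolute figure follows. One misplaced case adds about 1/100 = 1 point to an arm of 100.

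**The case against.** The strongest reply is that retention looks deliberate. PP removes major violations, and protocol 8.4 and 9.1.2 allow the operator to change device when the allocated one cannot be implanted. Table 2 of SAP 4.2.2 separates a switch after a real attempt from a non-allocated first device, and SAP 4.2 appears to expect crossovers inside PP. A set meaning eligible and started with the allocated device is coherent. This stands for the composite, and that rule should not change. It does not make the same set suitable for endpoints read off the implanted device.

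Second, the as-treated analysis is listed beside PP for every endpoint named here, and the safety population and supplemental tables follow the actual device. This is real mitigation. It is incomplete, because SAP 4.2 never defines an as-treated set or says that the safety population serves as one.

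Third, excluding crossovers is outcome-related selection after randomisation. This stands in full and limits what the corrected analysis can claim.

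A reader might infer three stronger things that the documents do not support:

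- That the main result or the PP composite is biased. Crossover is an event in both.
- That the SAP states the randomised label for PP. It is the likeliest reading, not a stated rule.
- That keeping crossovers must pull the devices together. Step 5 shows that this depends on who switches.

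**Conclusion.** The concern holds for a limited set of analyses: PP patency alone (45-day and 13-month CCTA, 45-day TEE) and PP DRT. It rests on the text of Table 2 in SAP 4.2.2, which is clear, and on an arm label that is inferred.

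The size cannot be fixed without a crossover rate. Under the borrowed rates and average-patency assumption, the loss is 0.8 to 2.0 points at 2% to 5% two-way crossover and 4.0 points at 10%. All are well inside the 13.3-point half-width, and the direction is not assured. For DRT the attribution matters more than the average shift.

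Severity is minor to moderate: supportive secondary analyses and one main safety outcome are affected.

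**What to change.** In SAP 4.2.2:

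1. Keep the current PP rule for the composite, and state that it retains crossovers by design and analyses them as randomised.
2. For the PP analyses of patency alone and DRT, add a row excluding patients whose final implanted device is not the randomised device, or who have none. Give this set its own name, so that the two PP sets are not confused.
3. Report the number excluded per arm.
4. Define an as-treated analysis by final implanted device, using the labelling rule of 4.2.3, and show it beside the PP result.

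The final device is already tabulated in the procedural characteristics table (SAP 5.5), so the programming cost is one filter. Imaging denominators fall by the number of crossovers and of patients left without a device.

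The SAP should also state the statistical cost. The exclusion occurs after randomisation and is tied to failed sealing or instability. It can flatter the device that fails more often by removing its hardest anatomies. The result should be labelled supportive and read with the intention-to-treat analysis.
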